RATIONALE	
A widely used semi-quantitative parameter to assess tumor status is the standardized uptake value (SUV). SUV estimation accuracy can be impacted by many variables. Today there still exists a significant amount of variability in PET/CT results in test and re-test studies. This variability can be introduced by instrumentation and subject-specific factors. Variability reduces image quality and increases the required changes in tumor quantification to reflect real tumor response or progression.
 
PET/CT scanning process requires that the entire net injected dose of radiolabeled tracer is administered intravenously as a bolus. The quality and quantification of a PET/CT image is highly dependent on the uptake of radiolabeled tracer. Boellaard et al. have indicated infiltrations could potentially underestimate SUV measurements by as much as 50%. Infiltrations and obstructions are not uncommon.

STUDY DESIGN	This is a prospective single-center study with no therapeutic intent.
PRIMARY OBJECTIVE	To characterize impact of moderate or greater infiltrations on standardized uptake values.
EXPLORATORY OBJECTIVES	
To estimate the impact that infiltrations may have on initial assessment and/or response assessment in accordance with PERCIST criteria.
 
To estimate the effect of moderate or greater infiltrations on metabolic tumor volume and total lesion glycolysis.

NUMBER OF SUBJECTS	The number of subjects will be determined based on the number of moderate or greater infiltrations at the site.
SUBJECT SELECTION CRITERIA	
Inclusion Criteria: Subjects with solid tumors or lymphoma undergoing PET/CT scan who have at least one measurable target lesion and sustain a moderate or greater infiltration.
 
Exclusion Criteria: Subjects unwilling or unable to tolerate a repeat PET/CT scan. Subjects with meaningful medical intervention between PET/CT scans that would likely impact SUV. Subjects with follow up moderate or severe injection infiltrations that would likely impact the SUV. Patients for whom an infiltration score cannot be determined, such as when ports or other central lines are used. Pregnant patients. Subjects who are not able to read/understand English.

DURATION OF SUBJECT PARTICIPATION AND DURATION OF STUDY	Patients who experience a moderate or greater infiltration will be invited for a repeat PET/CT scan. Subject participation in this study is limited only to the few minutes they are questioned after their first scan and before their repeat scan, and for the time it will take for the repeat scan. These questions are designed to try and ensure both scans were conducted under similar subject conditions (fasting levels, prior activity levels, etc.) The questions should not require more than 15 minutes total. Final data analysis will be completed within 3 months of enrolment of the final subject.
STATISTICS Primary Analysis Plan	Analyses will be descriptive in nature because the sample size of the group who will return for re-testing is challenging to forecast a priori. We anticipate enrolling up to 20 patients in 12 months based on the infiltration rate at WFB and accounting for ongoing quality improvement efforts.
Rationale for Number of Subjects	All subjects undergoing PET/CT who experience a moderate or greater infiltration will be invited back for a repeat scan.

1.0 INTRODUCTION AND BACKGROUND

PET/CT scanning is becoming progressively more important to the management of patients with cancer due to its accuracy and convenience in presenting anatomical and functional information. Oncology PET/CT scans are often used to stage cancer and assess therapy response. Quantification of PET/CT results is increasingly being used. A widely used semi-quantitative parameter to assess tumor status is the standardized uptake value (SUV). SUV estimation accuracy can be impacted by many variables. Therefore, producing high quality PET/CT images requires rigorous protocols of image acquisition and analysis.

Today, there still exists a significant amount of variability in PET/CT results in test and re-test studies [1]. This variability can be introduced by instrumentation and patient-specific factors. Variability reduces image quality and increases the required changes in tumor quantification to reflect real tumor response or progression. Weber's recent multi-center study of NSCLC found a 30% SUV decrease (in defining therapeutic response) or a 40% SUV increase (in defining progression) is required to have confidence that the results are indicative of metabolic response or metabolic progression, rather than a reflection of variability in the measurement of the PET/CT process [2].

Accurate SUV calculation requires that the entire net injected dose of radiolabeled tracer is administered intravenously as a bolus. The quality and quantification of a PET/CT image is highly dependent on the uptake of radiolabeled tracer. Boellaard et al. have indicated infiltrations could potentially underestimate SUV measurements by as much as 50% [3]. Infiltrations and obstructions are not uncommon. Single center studies have demonstrated that improper injections of radiolabeled tracer for PET can occur in 10 - 21% of cases [4, 5, 6].

Recent studies using a novel QA/QC tool (LaraTM System) for the radiotracer injection process revealed that current means to detect infiltration do not completely identify all infiltrations/obstructions [7]. Since infiltrations may not be visible in the standard field of view (FOV) and since the impact of a peripheral circulatory obstruction may not be visible even if an injection site is in the FOV, it is possible for reading and treating physicians to be unaware that a patient's image and quantification has been impacted. Additionally, when current means do detect an infiltration, they under-represent the severity because they are not capturing that infiltrations often resolve during the uptake period. As a result, infiltrations or obstructions may cause SUV inaccuracy and could adversely impact staging and tumor assessments.

The FDA-listed Lucerno Dynamics LaraTM System is comprised of sensors, a reader and software. The sensors are connected to a reader that provides temporary data storage. By using similar principles as PET scanning technology (i.e., scintillating crystal and photomultiplier), the sensors measure the presence of radiolabeled tracer in target areas of interest. The system software that has been developed uses time activity curves (TACs) to provide a way to determine whether radiolabeled tracers commonly used in PET/CT remain pooled near the injection site during the uptake period, rather

than circulating in the vascular system. Past and ongoing studies using standard PET/CT and dynamic images have confirmed the Lara™ System is a better tool than current imaging to identify and characterize the presence of radiotracer near the injection site during uptake. Because the Lara™ sensor is located near the injection site, it captures all infiltrations and obstructions and is agnostic to imaging FOV. With a one second frame rate, Lara™ dynamically captures radiotracer presence during the entire uptake period, and therefore better characterizes infiltrations as compared to static images taken at 60 minutes post injection. Lara's TAC feedback on the fidelity of an FDG injection of the entire uptake period could help reduce erroneous infiltration interpretations.

Because Lara will be able to better identify and characterize moderate or greater infiltrations, Lucerno will assist the clinical site in the design and execution of a study to assess impacts of these infiltrations. All medical management of subjects participating in this research is at the discretion of the site medical care team and is not part of the research protocol.

2.0 PURPOSE OF THE STUDY

A widely-used parameter to quantify uptake of radiolabeled tracer is the standardized uptake value (SUV), calculated by normalizing radiolabeled tracer activity concentration in a volume of interest (VOI) to the decay-corrected injected activity and body mass. SUVs allow semi-quantitative evaluation of disease and therapy response. Accuracy of SUV estimation assumes the entire net injected dose is administered intravenously as a bolus injection. Improper injections have been shown in previous studies to impact SUV measurements [3, 4]. In the few published studies measuring infiltration rates in PET, radiolabeled tracer infiltration occurs in 10–21% of clinical exams [4, 5, 6]. Phase 1 of an ongoing quality improvement project at Wake Forest Baptist Health using the Lara™ device has shown an infiltration rate of 13.3%. Additionally, infiltrations may impact a reading physician's ability to properly stage a patient's cancer, since metastatic lesions may not be visible in infiltrated cases.

The purpose of this study will be to characterize the impact of moderate or greater infiltrations on standardized uptake values.

2.1 Objectives of the study

2.1.1 Primary Objective

To characterize impact of moderate or greater infiltrations on standardized uptake values of solid tumors or lymphoma.

2.1.2 Exploratory Objectives

- To estimate the impact that infiltrations may have on initial assessment and/or response assessment in accordance with PERCIST criteria.
- To estimate the effect of moderate or greater infiltrations on metabolic tumor volume and total lesion glycolysis.

2.2. Anticipated duration of the study

Participation in the study is limited to the time from the baseline PET/CT to the repeat PET/CT scan which is anticipated to be no more than one week. While subjects will only answer questions for a total of less than 15 minutes to try and ensure the conditions for each PET/CT scan are standardized as much as possible, these two sessions of questions may be 1 to 7 days apart. Patient accrual will be closed after 12 months.

3.0 PROTOCOL

3.1 Protocol number and title

LUC-2017-001 A Study to Assess the Impact of Moderate/Significant Infiltrations on the Standardized Uptake Values of Target Lesions

3.2 Protocol version number and date

Version 0, December 19, 2017

3.3 Project design

This is a prospective, single-center, study with no therapeutic intent.

3.4 Subject selection

3.4.1 Inclusion criteria

Subjects with solid tumors or lymphoma undergoing F-18 FDG PET/CT scan who have at least one measurable target lesion and sustain a moderate or greater infiltration.

3.4.2 Exclusion criteria

- Subjects unwilling or unable to tolerate a repeat PET/CT scan.
- Subjects with meaningful medical intervention between PET/CT scans that would likely impact SUV.
- Subjects with follow-up moderate or greater infiltrations as determined by the PI and Lara score.
- Patients for whom an infiltration score cannot be determined, such as when ports or other central lines are used.

- Pregnant women.
- Subjects who are not able to read/understand English

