3.5 Study procedure

The LaraTM System is currently commercially available and is being used on site as part of a Quality Improvement project on all patients undergoing PET/CT studies. The LaraTM System will continue to be used on all patients undergoing PET/CT scans at the completion of the Quality Improvement Study to provide ongoing quality control and quality assurance of the injection process. Patients whose scans are determined by the Nuclear Medicine physician, or their designee, to have a moderate or greater infiltration based on review of the standard PET images and/or LaraTM TACs will be asked to return for a repeat PET/CT scan within 1-7 calendar days. In the event that the follow up scan shows any infiltration; the Nuclear Medicine physician or designee will be consulted to determine appropriate next steps. Site will duplicate the PET/CT protocol of the initial scan as carefully as possible for the follow up scan. Factors that will help ensure consistency of scan conditions to be recorded on the Case Report Form (CRF) (Appendix 1) include (but are not limited to):

- Same pre-procedure process and instructions to subject
- Time of day
- Glucose
- Time from injection to scanning
- PET/CT bed protocol
- Fasting and pre-scan activity level
- Subject weight
- BMI
- Prescribed FDG dose
- Flush volume
- Concomitant medications
- Any other data deemed pertinent by the technologist and/or Nuclear Medicine physician

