3.6.4 Data Analysis

Upon the determination of an infiltrated subject, the technical staff will notify the Nuclear Medicine physician to determine the severity and appropriateness of the subject for the study. To qualify for the study, the subject will need:

- at least one target lesion; and

- at least a moderate infiltration as determined by visual analysis and/or infiltration score from the Lucerno Dynamics' Lara™ system software

Data will be analyzed on each individual subject after the second imaging session. The scans will be presented in tandem such that simultaneous measurements may be performed using a qualified image analysis program, such as MIM version 6.5. Up to five target lesions will be assessed, chosen to include the target lesion or lesions defined under the PERCIST criteria [8]. For each lesion, SUV peak will be measured, and a volume contour will be created using mean liver SUV+2SD as a threshold., SUVmean, metabolic tumor volume, and total lesion glycolysis will be measured from the contour. The lesions chosen will be the same for each scan, however differences in the scans may affect the volume contour. Liver and blood pool measurements will also be made as for PERCIST criteria.

SUV will be descriptively compared for the original and re-test. Our expectation is that SUV will increase at the re-test, although we are not amply powered to conduct a rigorous statistical test. We will also evaluate the relationship between SUV values and the Lara score by computing a Pearson's correlation coefficient. We hypothesize this correlation will be positive.

We hypothesize that presence of venous stasis (a cessation or impairment of venous flow) may have an influence on the relationship on SUV scores. We will conduct a sensitivity analysis by conducting analyses with and without stasis cases. Specifically, we will compare the % change in SUV values between test and re-test and the correlation coefficient of % SUV change and Lara score in the samples including and excluding stasis cases.

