To assess the exploratory objective of whether extravasation of radiotracer could influence initial staging, for patients where the type of primary solid tumor is known the T, N, and M stages will be assessed to the extent possible by PET/CT for each scan and an overall stage assigned. This will be done even if the scan was performed for response assessment or follow up. No additional imaging or clinical information will be used and it is recognized that this assessment may not generate the true clinical stage. However, the comparison between the two scans will still provide information regarding the risk of changing stage based on missed or mischaracterized lesions after an extravasation event. To provide more granular information, the number of FDG avid regional nodes and number of FDG avid non-nodal metastases (capped at 25 each) will also be recorded for each scan.

For the exploratory objective of whether extravasation can influence apparent response to therapy, we will use the infiltrated and repeat scans to explore the impact of infiltrations on PERCIST criteria if there is an existing PET/CT scan for

comparison. This other PET/CT scan could either be a prior or a follow-on PET/CT scan that has a Lara-validated injection.

All scans will be analyzed by a qualified Nuclear Medicine physician and reported using the study imaging charter. Any measurements made for the clinical reports will not be used for this analysis. To mitigate bias, a second blinded radiologist will independently analyze the scans.

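### The SUV change between scans may include the continuing effect of treatment given before the first scan, and no planned analysis separates the two

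*Combined protocol and SAP*

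**What the plan says.** - **Who enters.** Section 3.4.1 admits "Subjects with solid tumors or lymphoma undergoing F-18 FDG PET/CT scan who have at least one measurable target lesion" and a moderate or greater infiltration. It sets no condition on earlier or current therapy.
- **Treatment exclusion.** Section 3.4.2 has one: "Subjects with meaningful medical intervention between PET/CT scans that would likely impact SUV".
- **Scan indication.** On the staging assessment, section 3.6.4 states: "This will be done even if the scan was performed for response assessment or follow up". The response objective in the same section also needs patients who have another PET/CT, earlier or later, for comparison.
- **Timing.** Under section 3.5, infiltrated patients "will be asked to return for a repeat PET/CT scan within 1-7 calendar days".
- **Main comparison.** Section 3.6.4: "SUV will be descriptively compared for the original and re-test". The stated direction is "Our expectation is that SUV will increase at the re-test, although we are not amply powered to conduct a rigorous statistical test". There are no non-infiltrated control pairs.
- **Sensitivity analysis.** Only one is planned, on venous stasis: "We will conduct a sensitivity analysis by conducting analyses with and without stasis cases". It covers the percentage SUV change and its correlation with the Lara score.
- **Partial safeguards.** The open-ended CRF list in section 3.5 includes "Concomitant medications". Under section 3.6.4 the Nuclear Medicine physician judges whether each subject is appropriate for the study.

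**The concern.** The within-patient comparison isolates infiltration only if the lesion itself is metabolically unchanged between the scans. The plan accepts this principle, since it excludes patients whose SUV may be altered by something done during the gap. But the exclusion is tied to when an intervention is given, not to when it acts. A patient scanned for response assessment may have had treatment before the first scan that is still changing lesion SUV some days later. As worded, the exclusion does not reach that patient.

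The infiltrated scan always comes first, so a drift shared by several patients is aligned with the contrast of interest and does not average out. If response is continuing, the re-test SUV is lowered and part of the tracer loss is hidden. If SUV is drifting upward, the loss is exaggerated. The pooled figure then depends on how many recently treated patients happen to be enrolled, and a reader cannot tell a minor infiltration effect from a changing tumour.

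**Working it through.** The plan states no figure on this point. The cap of 20 in section 3.6.3 is an accrual limit with no effect size or SD behind it, so there is nothing to reproduce. The calculation below only shows what size of drift would matter.

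**Inputs from the documents**
- Gap between scans: 1 to 7 days (section 3.5).
- SUV underestimation from infiltration: up to 50% (section 1.0).
- SUV decrease used to define response: 30% (section 1.0). This is a threshold set against measurement variability. It is not a rate of change.

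**Assumptions**
- A 30% fall, log-linear over W = 21 or 42 days, still under way at the first scan.
- Tracer losses of u = 10% and 20%, next to the cited maximum of 50%.

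**Formulas**
- Drift factor over a gap of g days: f = 0.70^(g/W).
- True re-test change: 1/(1 - u) - 1.
- Observed re-test change: f/(1 - u) - 1.

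**Drift factors**
- 7 days: 0.70^(7/21) = 0.888 (-11.2%); 0.70^(7/42) = 0.942 (-5.8%).
- 4 days: 0.70^(4/21) = 0.934 (-6.6%); 0.70^(4/42) = 0.967 (-3.3%).
- 1 day: 0.70^(1/21) = 0.983 (-1.7%); 0.70^(1/42) = 0.992 (-0.8%).

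**Observed change in an affected patient (W = 21 days / W = 42 days)**

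| Tracer loss u | True change | 7-day gap | 4-day gap | 1-day gap |
|---|---|---|---|---|
| 10% | +11.1% | -1.3% / +4.7% | +3.8% / +7.4% | +9.2% / +10.2% |
| 20% | +25.0% | +11.0% / +17.8% | +16.8% / +20.8% | +22.9% / +23.9% |
| 50% | +100.0% | +77.6% / +88.5% | +86.9% / +93.3% | +96.6% / +98.3% |

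**Upward drift.** Using 1/f at 7 days, a 10% loss reads +25.1% (W = 21) or +17.9% (W = 42) instead of +11.1%.

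**Group mean.** If a share s of patients is affected, the mean shifts by s(f - 1)/(1 - u). With s = 0.5 (assumed) and a 7-day gap:
- u = 10%: -3.2 points (W = 42) to -6.2 points (W = 21).
- u = 50%: -5.8 points to -11.2 points.

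For scale, with 20 patients and an assumed SD of 20 points for the percentage change, the 95% confidence half-width is 2.093 × 20/√20 = 9.4 points.

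**The case against.** The strongest reply is that the documents do not show such drift occurring at all. The sentence on response-assessment scans gives neither the share of such patients nor the time since their therapy, and a follow-up scan may come long after treatment. The 30% is borrowed from a different use. This stands: the size is unknown and the figures above are conditional.

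Several stronger readings are tempting, but the documents do not support them:
- **A reader might infer that the exclusion is the only protection.** It is not. The short gap bounds any drift, the physician reviews each subject, and concomitant medications are recorded. Treatment continued through the gap could also be read as already excluded. These safeguards remain partial: no criterion ties the physician's judgement to earlier therapy, and no analysis uses the recorded data.
- **A reader might infer that the plan will exaggerate the infiltration effect.** Continuing response works against the expected increase. Only upward drift inflates it, and opposite drifts in different patients partly cancel.
- **A reader might infer that the sign of the result could reverse.** In the table that needs a 10% loss, a 7-day gap and the 21-day assumption together. At 4 days the same patient reads +3.8%.
- **A reader might infer that the CRF lacks the needed items.** The form is not shown in the public text and the list in section 3.5 is not exhaustive, so this cannot be said.

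It is also fair that the study is small and descriptive, that liver and blood pool are measured on both scans, and that nothing suggests drift would track the Lara score, so it would mainly add noise to that correlation. But the plan does not commit to using the liver and blood-pool values for this purpose. A descriptive estimate still needs to say what it is an estimate of.

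**Conclusion.** The concern holds as a gap in the analysis, not as a demonstrated bias. Any treatment-driven SUV change over the 1 to 7 days enters the original versus re-test difference in a fixed scan order, and nothing planned separates it from tracer loss. The direction is not determined.

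Under the stated assumption, drift at a 7-day gap is about the size of the change produced by a 10% tracer loss or about half of it (-11.2% or -5.8%, against +11.1%). At a 1-day gap, or against a 50% loss, it is minor. The conclusion that the split is worth reporting rests only on the wording of sections 3.4.2, 3.5 and 3.6.4. The percentages rest on the assumed drift.

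**What to change.** 1. **CRF.** Make sure it captures the scan indication and the type and date of the last anticancer treatment before the first scan. It may already do so.
2. **Section 3.6.4, main summary.** Keep all pairs.
3. **Section 3.6.4, sensitivity analysis.** In the with/without format already planned for stasis, report the percentage SUV change and its correlation with the Lara score for all pairs, and again for pairs from patients with no prior treatment (initial staging). This needs no cut-off for time since treatment.
4. **Listing.** For the remaining patients, list percentage SUV change against days since last treatment and days between scans. Fix any further grouping by time since treatment before SUVs are measured.

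This excludes nobody, sets no clinical rule and leaves the cap of 20 unchanged. The cost is at most a few CRF items and one extra descriptive split. The untreated subset will be smaller than the maximum of 20 and of unknown size, so its estimate will be less precise and should be read as a check on the main summary, not as a replacement for it.

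### No stated rule covers a re-test with sub-moderate infiltration, although the re-test is the comparator for the primary SUV comparison; where such pairs are kept, the measured impact shrinks

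*Combined protocol and SAP*

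**What the plan says.** Section 2.0 gives the premise: "Accuracy of SUV estimation assumes the entire net injected dose is administered intravenously as a bolus injection". Section 3.6.4 builds the primary comparison on it. "SUV will be descriptively compared for the original and re-test", and the direction is anticipated: "Our expectation is that SUV will increase at the re-test, although we are not amply powered to conduct a rigorous statistical test".

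Three places deal with infiltration at the re-test.

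- Section 3.4.2 lists as an exclusion: "Subjects with follow-up moderate or greater infiltrations as determined by the PI and Lara score".
- The synopsis words the same exclusion differently: "Subjects with follow up moderate or severe injection infiltrations that would likely impact the SUV".
- Section 3.5 says: "In the event that the follow up scan shows any infiltration; the Nuclear Medicine physician or designee will be consulted to determine appropriate next steps".

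Section 3.6.4 does not mention the quality of the re-test injection. Its planned correlations refer to the Lara score without saying which injection is meant. Its one sensitivity analysis repeats the results with and without venous stasis cases.

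**The concern.** The contrast between original and re-test measures the impact of infiltration only to the extent that the re-test dose was delivered. Neither version of the exclusion reaches a re-test infiltration below moderate. The consultation in section 3.5 does cover it, but states no criterion and no consequence for the analysis set. Such a pair may be kept or dropped, and the plan does not say which. The decision would also be taken after the follow-up scan has been done, which is a further reason to fix the analysis rule in advance.

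If the pair is kept, the error has one direction: tracer lost at the re-test lowers the comparator, so the observed rise is too small. The severity analysis is affected too. The percentage change in SUV depends on both injections, so relating it to the score of one injection adds scatter that has nothing to do with the severity of the original infiltration. With at most 20 patients, a few such pairs can matter for patient-level results and for a Pearson coefficient.

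**Working it through.** The plan has no calculated figure to reproduce. The cap of 20 in section 3.6.3 is an accrual limit, with no effect size, standard deviation or power behind it. The check is therefore algebra on the primary contrast, followed by a range of inputs.

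**Inputs from the documents**

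- Largest SUV underestimate attributed to infiltration: 50% (section 1.0).
- Infiltration rate: 13.3% at the site (section 2.0) and 10–21% published (section 1.0), neither split by severity.
- Maximum number of patients: 20 (section 3.6.3).

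**Assumptions**

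- Net SUV loss at the original scan, L: 20–50%. Only the 50% is in the documents.
- Net SUV loss at a sub-moderate re-test, m: 2–10%. Not in the documents.
- Share of analysed re-tests affected, q: 10–21%. This borrows the all-grade rates above for lack of anything better.

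**Formulas.** Let S be the SUV with the whole dose delivered. The original scan reads S(1 − L) and the re-test reads S(1 − m).

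- Change with an intact re-test: 1/(1 − L) − 1 = L/(1 − L)
- Change observed in an affected patient: (1 − m)/(1 − L) − 1 = (L − m)/(1 − L)
- Relative shortfall in that patient: m/L
- Cohort mean with common L and m: L/(1 − L) − q·m/(1 − L)
- Relative shortfall of the mean: q·m/L

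**Results** (triplets are for q = 10%, 13.3%, 21%)

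| L | m | Intact change | Affected patient | m/L | Cohort mean change | Relative shortfall of mean |
|---|---|---|---|---|---|---|
| 20% | 2% | 25.0% | 22.5% | 10% | 24.8 / 24.7 / 24.5% | 1.0 / 1.3 / 2.1% |
| 20% | 5% | 25.0% | 18.8% | 25% | 24.4 / 24.2 / 23.7% | 2.5 / 3.3 / 5.2% |
| 20% | 10% | 25.0% | 12.5% | 50% | 23.8 / 23.3 / 22.4% | 5.0 / 6.7 / 10.5% |
| 30% | 5% | 42.9% | 35.7% | 17% | 42.1 / 41.9 / 41.4% | 1.7 / 2.2 / 3.5% |
| 50% | 2% | 100% | 96.0% | 4% | 99.6 / 99.5 / 99.2% | 0.4 / 0.5 / 0.8% |
| 50% | 5% | 100% | 90.0% | 10% | 99.0 / 98.7 / 97.9% | 1.0 / 1.3 / 2.1% |
| 50% | 10% | 100% | 80.0% | 20% | 98.0 / 97.3 / 95.8% | 2.0 / 2.7 / 4.2% |

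The extremes for the mean are 0.10 × 0.02/0.50 = 0.4% and 0.21 × 0.10/0.20 = 10.5%.

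**Number of pairs.** Among 20 re-tests, 20 × 0.10 = 2.0, 20 × 0.133 = 2.7 and 20 × 0.21 = 4.2 would be affected. The chance of at least one is 1 − (1 − q)^20 = 88%, 94% and 99%. The source rates count all grades, so for sub-moderate events alone these figures are more likely too high than too low, unless patients who have infiltrated once are more prone to do so again. The documents are silent on that.

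**The case against.** The strongest reply is that section 3.5 already deals with the matter. Every follow-up scan with any infiltration goes to a physician, who may well drop it. This stands in part. A reader might infer that the plan keeps mildly infiltrated re-tests as a fixed rule, and it does not say so; their status is simply open. The reply does not supply an analysis rule, however.

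A second tempting inference is that the exploratory PERCIST analysis holds its comparator to a stricter standard than the primary analysis does, because section 3.6.4 says there: "This other PET/CT scan could either be a prior or a follow-on PET/CT scan that has a Lara-validated injection". The documents do not support this. The term is not defined and could mean an injection monitored by Lara and found below the moderate threshold, which is what the re-test already has. The PERCIST comparator may also be a prior scan, which could be why the condition is spelled out there.

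Third, the size rests on assumptions. The case in which the rise is halved (25.0% to 12.5%) is one hypothetical patient whose mild loss is half of a moderate-or-greater loss; it is not a study result. The site rate comes from the first phase of a quality improvement project, and section 3.4.3 says steps have since been taken to reduce infiltrations. Section 1.0 notes that infiltrations often resolve during uptake, so a mild event need not cost a fixed share of the dose. All of this stands, and it is why the size is given only as a conditional range.

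Finally, the study is descriptive and expressly not powered, the shift in the mean is small beside the 30–40% SUV changes cited in section 1.0, and the error runs against the expected direction, so it cannot manufacture an effect. That limits the importance of the point. It does not remove the case for a nearly free safeguard.

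**Conclusion.** The point holds in limited form. No stated rule excludes a re-test with sub-moderate infiltration from the primary comparison, and no planned analysis shows what such pairs do to the result. Where they are kept, the bias is toward no effect. In an affected patient the shortfall is m/L, which runs from 4% to 50% over the assumed ranges. For the cohort mean it is about 0.4–10.5% in relative terms, or q·m/(1 − L) = 0.25 to 4.2 percentage points of SUV change.

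These sizes rest on assumed losses and on an all-grade infiltration rate used for sub-moderate re-tests, with common L and m across patients. The documents establish the gap and the direction. They do not establish that the study's estimate will be materially understated, and a reader should not conclude that it will. This is a cheap improvement, not a flaw that undermines the study.

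**What to change.** In section 3.6.4, state that:

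1. the Lara score of both injections is reported for each patient;
2. the original versus re-test SUV comparison, and the correlation of percentage SUV change with the Lara score of the original scan, are given for all eligible pairs;
3. both are repeated without pairs whose re-test shows any infiltration on Lara or on the images, in the same way as the planned stasis sensitivity analysis.

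The correlation should use the original-scan score, not the difference between the two scores. Nothing in the documents shows that the Lara score is linear in lost dose, so a difference has no established meaning.

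The synopsis exclusion, section 3.4.2 and section 3.5 should also be reconciled so that they read as one rule on which pairs enter the analysis. This concerns the analysis only and leaves any decision on re-scanning as it is.

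The cost is a few sentences. Section 3.5 says Lara is used on all PET/CT patients at the site, and section 3.4.2 excludes patients whose score cannot be determined, so the re-test scores should already exist; the case report form may already record them. The downside is a restricted analysis with a few fewer patients: about 2 to 4 of 20 at the rates used above, probably fewer.
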